7.4.3. Interim Analyses

An interim analysis with stopping criteria for futility and validation of sample size is planned after 50% of the participants have completed the primary endpoint assessment at Day 30 (Visit 4).

To prevent power loss due to this interim analysis, a beta-spending function was used to calculate stopping bound according to O'Brien and Fleming (Lan, 1983) (O'Brien, 1979). The futility bound for difference in proportions between active treatments and placebo is 0.0232 in the interim analysis. The nominal level of significance is not affected α =0.05 (two-sided) and 90% power is kept for the final analysis. The interim analysis will be performed on the Full Analysis set.

If the primary endpoint is missing at Day 30, the participant will be excluded from the interim analysis (Complete Case Analysis). The interim efficacy analysis will be performed using a two-group chi-square test comparing the FCI combination with placebo followed by the FC–placebo comparison.

If the study is not stopped due to futility after the interim look, the assumptions for the sample size determination will be checked and the sample size may be increased if a decrease in treatment difference by more than 10% (due to a lower placebo rate and/or due to a higher rate in the active arms) is observed.

The SAP will describe the planned interim analyses in greater detail.

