Statistical Methods: The study will aim to enroll up to 1465 participants, which assumes a 10% screen failure rate, with a final allocation of 659 participants in the treatment arm and 659 in the control arm.

This sample size of ensures a power of 90% at a 2-sided α of 5%, assuming a 1:1 randomization, a placebo rate of 6% (of participants with at least one COVID-19–related medically attended contact, due to increased symptom severity, or incidence of death due to COVID-19 through Day 30) and an assumed relative risk reduction of 65% to 2.4% in the active treatment arms. The statistical test of the null hypothesis of no between-group difference in proportions, as specified

in the primary endpoint, will be tested using a χ^2 test at a two-sided 5% significance level. An interim analysis for futility will be performed after 50% of participants have completed the primary endpoint assessment at day 30. Safety analyses will be performed on the Safety Population, consisting of all participants who are randomized and received study drug, analyzed by actual treatment arm. A more detailed description of the statistical methods can be found in Section 7.

Protocol Title: A virtual Phase 2 randomized, placebo-controlled, double-blind study to evaluate the safety and efficacy of the combination of famotidine and celecoxib as a post-exposure prophylaxis (PEP) for newly-infected COVID-19 patients.

Short Title: LEAP-CT as a post-exposure prophylaxis for newly-infected COVID-19 patients.

Rationale: Please refer to the Master Protocol LDOS-21-001 for a comprehensive background and rationale for this study of a combination of famotidine and celecoxib as post-exposure prophylaxis (PEP) for newly-infected COVID-19 patients.

Overall Design: This is a Phase 2, randomized double-blind placebo-controlled decentralized virtual study in which outpatient participants, newly diagnosed for COVID-19, will be randomized in a 1:1 ratio to one of two study groups (1 treatment group and 1 control group). The study is designed as a virtual trial in that it will be conducted, *in situ*, with home-based participants entering self-assessments via a web-enabled adaptive platform – The participants will be under the oversight of regionally based investigators who will be responsible for study conduct and the review of blinded data on a periodic basis.

Intervention Groups and Duration: The treatment regimen for this study is shown in Table 4.

Regimen	Dose	# of Participants

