7.2. Sample Size Determination

The sample size was estimated assuming that an interim analysis with stopping criteria for futility will be performed after 50% of participants have a primary endpoint assessment at Day 30. The O'Brien-Fleming beta-spending function is used to determine the non-binding futility boundary.

A total of 1318 evaluable participants, defined as part of the Full Analysis population (659 per group) are required to detect a relative reduction in the primary efficacy parameter of 60% in the active treatment arms compared to placebo (from of 6% in the placebo group to 2.4% in the active groups) with 90.0% power and using a two-sided χ^2 -test with 0.5% significance level, assuming variances are pooled, and that continuity correction was not used. Assuming a 10% screen failure rate, 1465 enrolled participants will be required.

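### The interim futility bound of 0.0232 is not the O'Brien-Fleming beta-spending bound it is said to be (about 0.004), has no stated direction, and if followed as a required benefit cuts power to about 77-78%

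*Protocol*

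**What the plan says.** Protocol Section 7.2 bases the sample size on one futility look after half of the participants have a Day-30 assessment: "The O'Brien-Fleming beta-spending function is used to determine the non-binding futility boundary". The design inputs there are 6% on placebo, 2.4% on active, 659 evaluable participants per group and 90% power.

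Section 7.4.3 says that "a beta-spending function was used to calculate stopping bound according to O'Brien and Fleming", and that its purpose is to avoid losing power. It then gives the threshold: "The futility bound for difference in proportions between active treatments and placebo is 0.0232 in the interim analysis". It adds that the 5% two-sided level is unaffected and that "90% power is kept for the final analysis". If the trial continues, "the sample size may be increased if a decrease in treatment difference by more than 10" per cent is observed.

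No sign or direction is attached to 0.0232. The hypotheses in Section 7.1 write the difference as active minus placebo, so a benefit is negative.

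**The concern.** The figure looks too large for its stated origin. An O'Brien-Fleming spending function uses little beta at half information, so its futility bound should lie near zero benefit. Here the bound is 0.0232/0.036 = 64% of the assumed effect. It is even above the observed difference needed for significance at the final analysis (about 0.0217).

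The missing sign adds a second problem. The number can mean stopping unless active is at least 2.3 points better, or stopping only if active is at least 2.3 points worse. For any interim result between these two values, the two readings give opposite decisions.

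This is the only numerical criterion in the protocol for a decision that can end the trial. On the first reading an effective treatment is at risk of being abandoned. On the second the look does little to detect futility.

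**Working it through.** **Inputs.** Rates 6% and 2.4% (difference 0.036), 659 per group and 90% power: Section 7.2. Look at 50%, so 329.5 per arm, and two-sided 5% alpha: Section 7.4.3. Final test, pooled chi-square without continuity correction: Section 7.4.2.

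**The design reproduces at 5% alpha.** The fixed-sample requirement is about 651 per group. At 659 with no look, power is 90.4% (normal approximation) or 91.5% (binomial simulation). The inputs are therefore the right ones for checking the bound.

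**The stated bound does not reproduce.**

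1. Beta spent at t = 0.5 (Lan-DeMets O'Brien-Fleming form, beta 0.10): 2 × [1 − Φ(1.645/√0.5)] = 0.0200.
2. Interim standard error: √[(0.06 × 0.94 + 0.024 × 0.976)/329.5] = 0.01556.
3. Bound, placebo minus active: 0.036 − 2.054 × 0.01556 = 0.0040. Pooled variance gives 0.0039. Other O'Brien-Fleming forms give roughly 0.000 to 0.008.
4. Ceiling if all beta is spent at the interim: 0.036 − 1.2816 × 0.01556 = 0.0161.
5. Spend implied by 0.0232: Φ[(0.0232 − 0.036)/0.01556] = 0.205, twice the total beta.

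**Other inputs in the protocol.** The ceiling is the largest bound that any beta-spending function could give.

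| Input changed | Interim n per arm | Ceiling |
|---|---|---|
| None (6% vs 2.4%) | 329.5 | 0.0161 |
| Half of the 1465 enrolled | 366 | 0.0171 |
| 65% reduction (6% vs 2.1%) | 329.5 | 0.0194 |
| Both of the above | 366 | 0.0204 |
| 0.5% significance level, with the 1036 per group it would need | 518 | 0.0201 |

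The 65% comes from the Synopsis, which gives an "assumed relative risk reduction of 65% to 2.4% in the active treatment arms", although a 65% reduction from 6% is 2.1%. The 0.5% level is printed in Section 7.2. Pocock, linear and Hwang-Shih-DeCani spending with beta 0.10 give bounds of about 0.001 to 0.012. O'Brien-Fleming spending with beta 0.20 gives 0.013. None reaches 0.0232.

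**Final critical difference.** 1.96 × √(2 × 0.042 × 0.958/659) = 0.0217, below the interim bound.

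**Operating characteristics.** Stopping probabilities are from exact binomial enumeration with 330 per arm.

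| | Bound 0.004, benefit required | 0.0232, benefit required | 0.0232, active minus placebo |
|---|---|---|---|
| Stop, 6% vs 2.4% | 2.0% | 19.7% | 0.005% |
| Stop, no effect, both arms 6% | 59.7% | 89.1% | 10.9% |
| Stop, no effect, both arms 4.2% | 61.5% | 92.8% | 7.2% |
| Power, normal approximation | 89.8% | 76.7% | 90.4% |
| Power, simulation | 90.9% | 77.9% | 91.5% |

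Power assumes 659 per group, the rule always followed and no sample-size increase. The normal figures use a bivariate normal with correlation √0.5 and a final critical value of 1.96.

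On the required-benefit reading, 91.5% − 77.9% = 13.6% of all trials with the assumed effect stop although they would have ended significant. That is 13.6/19.7 = 69% of the stopped trials.

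**The case against.** **The bound is non-binding.** This is correct, and it means crossing the bound does not oblige a stop and type I error is not inflated. It protects alpha, not power: power is lost whenever the rule is followed. The 77-78% is the result of always following it.

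**The direction can be inferred.** Section 7.4.3 attributes a smaller treatment difference to a lower placebo rate or a higher active rate. That treats the difference as a positive benefit, so the active-minus-placebo reading has less support and the missing sign is secondary. This stands, but it points to the reading that loses power.

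**The SAP may set the boundary correctly.** Interim detail is deferred to the SAP, which is not available here. The protocol nevertheless fixes the number and the power claim itself, and a correct SAP would then contradict it.

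**The sample size can be increased.** This applies only if the trial is not stopped, so power is still capped at the probability of continuing, about 80%.

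**The sample size is adequate.** By normal approximation, a non-binding bound of this form needs about 664-665 per group for 90% power. Simulation gives 90.9% at 659. The objection stands: the correction creates no need for more participants.

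**The figure may come from another design.** Sections 7.1 and 7.4.3 still refer to two active comparisons in a two-arm trial. The document does not show where 0.0232 came from.

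**Conclusion.** The concern holds. Under the stated method and inputs the futility bound is about 0.004, and 0.0232 as a required benefit is incompatible with any beta-spending function that keeps 90% power. If the rule is always followed on that reading, power falls by about 14 points, to 76.7% (normal) or 77.9% (simulation). Read as active minus placebo, alpha and power are kept, but the rule is still not the stated boundary and rarely stops a drug with no effect.

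The power figures assume 6% against 2.4%, 659 per group and 330 per arm at the look. With the Synopsis's 65% reduction (2.1% on active), power would be about 83% against 95% without the look, and the implied spend of 15% would still exceed 10%. The exact replacement value depends on the O'Brien-Fleming form chosen.

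**What to change.** The sponsor should trace the inputs behind 0.0232 and recompute the bound from the stated function, naming its exact form. A value near 0.004 (placebo minus active, at 659 participants with Day-30 data) is expected. Section 7.4.3 should replace 0.0232, say in words which difference is meant and on which side of the bound the trial may stop, and keep the bound non-binding. Sections 7.2 and 7.4.3 should restate the power at 659 per group under the corrected bound and say whether it comes from a normal approximation or from simulation.

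The cost is one recomputed number, one sentence on direction and a restated power figure, carried into the SAP and the DSMB material. The trade-off is that an ineffective treatment would be stopped at the interim about 60% of the time, against about 89-93% under a 0.0232 required-benefit rule.

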7.4.4. Independent Data Safety Monitoring Board (DSMB)

The DSMB activities are described in **Section 7.1.1** of the Master Protocol (**LDOS-21-001**). The delivered information will contain un-blinded information and will therefore be prepared by an unblinded statistician team from the CRO (**Control of Control of Control**

8. SUPPORTING DOCUMENTATION AND OPERATIONAL CONSIDERATIONS

8.1. Appendix 1: Regulatory, Ethical, and Study Oversight Considerations

8.1.1. Regulatory and Ethical Considerations

This study will be conducted in accordance with the protocol and with appropriate principles of patient protection, as detailed in the **Section 8.1.1**of the Master Protocol (**LDOS-21-001**).

8.1.2. Financial Disclosure

Investigators and sub-investigators will provide the Sponsor with sufficient, accurate financial information, as requested, to allow the Sponsor to submit complete and accurate financial certification or disclosure statements to FDA. Investigators are responsible for providing information on financial interests during the course of the study and for 1 year after completion of the study.

8.1.3. Informed Consent Process

- The informed consent process for this study will be entirely virtual and done via phone call between the participant and site investigator. No in-person consenting will be performed.
- Upon initiating contact with the study staff, the prospective participant will be contacted by the site Investigator via phone call. The participant will be advised by the Investigator \on the nature of the study, and answer all questions regarding the study. If the prospective participant is deemed potentially qualified, the Informed Consent will be administered.
- Participants must be informed that their participation is voluntary. Participants will be required to sign a statement of informed consent that meets the requirements of 21 CFR 50, local regulations, ICH guidelines, Health Insurance Portability and Accountability Act (HIPAA) requirements, where applicable, and the IRB or study center.
- The participant will sign the informed consent using **an electronic** an electronic method that will capture the electronic signature of the participant and the PI. The authorized person administering the informed consent must also sign the ICF.
- The medical record must include a statement that written informed consent was obtained before the participant was enrolled in the study and the date the written consent was obtained. The authorized person obtaining the informed consent must also sign the ICF.
- Participants must be re-consented to the most current version of the ICF(s) during their participation in the study.
- A copy of the ICF(s) must be provided to the participant.

8.2. Appendix 2: Data Management

For this study, a secure, adaptive, interactive data collection platform, will be used. Because the platform is web-enabled, it provides a means for real-time data entry by the participantthrough any device that can access the internet. The participant is able to enter their ratings of symptom status and impact, and will be provide choices in drop-down menus, which evolve, based on prior responses.

8.2.1. Data Protection

Data protection considerations are provided in **Section 8.1.4** of the Master Protocol (**LDOS-21-001**).

8.2.2. Dissemination of Clinical Study Data

Clinical study data dissemination is addressed in **Section 8.1.6** of the Master Protocol (**LDOS-21-001**).

8.2.3. Data Quality Assurance

Data quality assurance is addressed in Section 8.1.7 of the Master Protocol (LDOS-21-001).

8.2.4. Source Documents

Information pertaining to source documents, including definition, is addressed in **Section 8.1.8** of the Master Protocol (**LDOS-21-001**).

8.2.5. Study and Site Closure

Study and site closure is addressed in Section 8.1.9 of the Master Protocol (LDOS-21-001).

8.2.6. Publication Policy

Guidelines pertaining to publication of study results are detailed in **Section 8.1.10** of the Master Protocol (**LDOS-21-001**).

8.3. Appendix 3: Adverse Events: Definitions and Procedures for Recording, Evaluating, Follow-up, and Reporting

A detailed overview of Adverse Event information is provided in **Appendix 2** of the Master Protocol (**LDOS-21-001**).

8.4. Appendix 4: Self-Rating of Symptoms and Symptom Scoring

A detailed overview of **based** -based self-rating of symptoms and symptom scoring is provided in **Appendix 3** of the Master Protocol (**LDOS-21-001**).

